### **8.9.2 Data analysis/description**

Descriptive statistics will be employed for the socio-demographic characteristics of the study population.

The primary efficacy endpoints, overall survival (OS) and event-free survival (EFS) will be compared descriptively to a group of ADA-SCID patients treated by allogeneic HSCT (historical control group). The main secondary endpoint, will be summarised descriptively.

Data will be summarized in tables displaying the mean, standard deviation, median, minimum, maximum and number of subjects per group for continuous data (e.g. age, weight) or in tables displaying count and percentage for categorical data (e.g. gender, previous treatment). Data will be presented by visit, if applicable. Data listing by subject will be provided as appropriate.

All statistical analyses will be performed and data appendices will be created using SAS® version 9.4 or higher

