### 3. Data to be collected

GOSH holds a registry / clinical database (European Society for Immunodeficiencies (ESID) and European Society for Blood and Marrow Transplant (EBMT) Registry, GOSH BMT clinical database) displaying information on these types of patients. Patients treated with HSCT have been identified who received a transplant at GOSH between 2000-2016. . ESID and EBMT will allow us to collect the below information:

- Demographics (gender, date of birth, date of death if any),
- Method of ADA-SCID diagnosis,
- HSCT treatment(s) including: date of treatment, transplant cells, donor type and outcome

However, to make this historical control group valid for marketing authorisation application, our discussions with regulatory agencies suggests that we need to collect further information valuable to compare the efficacy and safety of any new treatment in research vs. current HSCT standard of care as:

- Previous PEG-ADA ERT (and duration of treatment),
- Previous or current immunoglobulin therapy,
- Listing of relevant medical history, including infections (severe or opportunistic infections)
- Vaccination history and immunological response to vaccination

- Auto-immune disease
- Malignant disease / leukaemia
- Graft versus host disease
- ADA activity and ADA metabolites
- AEs and SAEs

This information is only available from the patient's records; we therefore plan to re-consent these patients to access their full medical records.

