Physical examination	Cardiovascular system Respiratory system Ear, Nose, Throat, Neck and Eyes (only at PreGT, 36 m) Neurological System (only at PreGT, 36 months) Abdominal Skin Other	X		X	X	X	X	X	X	X	X	X	X
Infection status	Evaluate any active infection at time of visit (respiratory tract, meningitis, sepsis, skin and mucosa, ear, nose and throat, abscess, persistent fever, other) Evaluate if there is any infection resulting in hospitalisation since last visit	X		X	X	X	X	X	X	X	X	X	X
PEG-ADA ERT status	Confirmation that if PEG-ADA has been administered or not since last visit	X		X	X	X	X	X	X	X	X	X	X
Blood Count	Haemoglobin, Platelet count White cell count Neutrophil count Lymphocyte count	X		X	X	X	X	X	X	X	X	X	X

Assessment	Result to be reported on the CRF	PreGT	Treatment	1	1.5	3	6	9	12	18	24	30	36
Lymphocyte subset counts	CD 3 CD19 CD16+ CD 56+ CD3+ CD4+ CD3+ CD8+ Naïve: CD4+CD45RA+CD27+	X		X	X	X	X	X	X	X	X	X	X
T cell function PHA stimulation**	Normal/Abnormal	X				X	X		X	X	X		
Lymphocyte function CD3 stimulation**	Normal/Abnormal								X			X	
GAM ***	Ig G level Ig A level Ig M level Immunoglobulin status since last visit	X						X	X	X	X	X	X
TRECS	TRECS on T cells TRECS on MNCs	X						X		X		X	
Vβ Spectratyping	Reported as Normal/Abnormal							X		X	X	X	X
Vector copy number in cells (qPCR)	vector copy number in PBMC vector copy number in CD34 vector copy number in CD3 vector copy number in CD19 vector copy number in myeloid						X	X		X		X	
Integration analysis	Normal/Abnormal						X****	X****		X		X****	X
Tetanus vaccination responses	Normal/Abnormal											X	X
ADA metabolite analysis (dATP) and ADA activity	Plasma deoxyadenosine level ADA (rbc) level dATP level	X		X	X	X	X	X	X	X	X	X	X
RCL (blood)	Reported as detectable / not detectable	X				X****	X****		X		X****		X

Assessment	Result to be reported on the CRF	PreGT	Treatment	1	1.5	3	6	9	12	18	24	30	36
Bone marrow aspirate for vector copy number qPCR and integration analysis (optional)	Morphology (Normal/ Abnormal) Vector copy number in BM-MNC Integration analysis (Normal / Abnormal)								X		X		X
Immunology save serum & SCLN (stored cells)	Serum collection date SCLN s collection date	X						X		X	X	X	X
Reporting of Adverse Event			X	X	X	X	X	X	X	X	X	X	X
Reporting of Concomitant Treatment ^^			X	X	X	X	X	X	X	X	X	X	X

^Lab results to be entered into eCRF for these time points should be the ones closer to the consent date/ visit date

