## 7 Analysis Populations

### 7.1 Efficacy Population

#### IMP Treated Subjects

The study protocol recruited 10 subjects with a diagnosis of ADA-SCID to be treated with IMP at GOSH. These subjects will be known as the “on-study” subjects.

In addition, a group of subjects were treated under a Compassionate Use Programme (CUP under GOSH Special License) either because the study was not yet open and urgent treatment was needed, because they were outside of the inclusion/exclusion criteria or because they followed a different process (i.e., received the IMP in two infusions). These subjects followed the same study schedule as the on-study subjects.

The primary efficacy population for analysis will consist of the on-study IMP treated subjects. A secondary efficacy population will consist of all IMP treated subjects (on-study and CUP)

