## 8.2.16 Exposure

Duration of follow-up in months will be calculated for the IMP treated subjects as:

$$12 * (\text{date of final evaluation} - \text{date of infusion} + 1) / 365.25.$$

For the HSCT controls, the duration of follow-up will be recorded on the eCRF.

Duration of follow-up will be summarized for the IMP treated and the HSCT control groups using descriptive statistics. In addition, the total subject-years of follow-up in each treatment group will be presented.

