### 8.3.2.2 Use of Immunoglobulin Replacement Therapy

The time to cessation of IgRT will be calculated (in months) as:

$12 * (\text{stopping date of IgRT} - \text{date of transplant}) / 365.25$ ,

or, for HSCT control subjects for whom the dates were not recorded, as:

age in months when IgRT stopped – age in months at transplant.

Time to cessation of IgRT will be summarised for each of the IMP treated and HSCT control groups using descriptive statistics and, if appropriate, estimated from a Kaplan-Meier curve in which subjects who are still receiving IgRT will be censored at the time of their last visit.

The number (%) of subjects who have stopped treatment with IgRT at 12, 18, 24, 30 and 36 months without restarting at any subsequent time point will be summarized for each of the IMP treated and HSCT control groups (data permitting) along with exact 95% CIs.

In addition, serum immunoglobulin levels (IgG, IgA and IgM) will be measured at each visit for the IMP treated subjects. Levels of IgG, IgA and IgM and changes from baseline will be summarised by visit using descriptive statistics. In addition, plots of the median value and range over time on a logarithmic scale will be produced for each parameter along with individual plots for each subject which will include age-dependent normal ranges provided by the study site.

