### **8.3.2.3 Rate of Severe Infections**

Infections will be recorded as adverse events. The infections of interest in this study are severe infections or opportunistic infectious episodes, defined as infections requiring hospitalization or prolonging hospitalization and/or documented infections by opportunistic pathogens (e.g. interstitial pneumonia, intractable diarrhoea).

The number (%) of subjects reporting severe infections or opportunistic infectious episodes along with the number of events reported will be summarized for each of the IMP treated and HSCT control groups (data permitting). In addition, the infection rate will be calculated as the number of infections/the total follow-up time. The rate will be calculated both within each treatment group and for each individual subject. The subject infection rate will be summarized by treatment group using descriptive statistics. In addition to the rate for the entire follow-up period, the rate will be calculated for both the first 12 months following transplant and for the second and third years.

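### The IgRT landmark percentage looks ahead for restarts over a varying period, so it measures something other than the stated objective; the optional Kaplan-Meier curve has no rule for death on IgRT

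*SAP*

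**What the plan says.** SAP 8.3.2.2 sets two summaries of IgRT use, each for the IMP and HSCT groups.

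- **Landmark percentage.** The number and percentage who have "stopped treatment with IgRT at 12, 18, 24, 30 and 36 months without restarting at any subsequent time point", with exact 95% CIs and, for controls, as far as the data allow. No end is given for the period in which a restart counts.
- **Time to cessation.** Descriptive statistics and, where judged suitable, a Kaplan-Meier curve in which "subjects who are still receiving IgRT will be censored at the time of their last visit". Death is not mentioned.

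Other relevant text:

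- **Objective** (Protocol 4.2.2, SAP 4.2): the percentage of IMP patients who require IgRT at each evaluation point from 18 months.
- **Status of the endpoint.** Protocol 8.9.2 names IgRT use as its main secondary endpoint and says "The main secondary endpoint, will be summarised descriptively". SAP 6 compares it with HSCT at the 12-month, 2-year and 3-year analyses.
- **Follow-up.** On-study subjects are followed for 3 years after infusion (Protocol 2). Controls were transplanted in 2000-2016 (Protocol Appendix 8). "For the HSCT controls, the duration of follow-up will be recorded on the eCRF", with no cap stated (SAP 8.2.16).
- **Data.** The visit schedule for IMP subjects records "Immunoglobulin status since last visit". The item to be collected for controls is "Previous or current immunoglobulin therapy" (Protocol Appendix 8), with no visit schedule or date limit.
- **Contrast.** For infections, the next SAP section adds that "the rate will be calculated for both the first 12 months following transplant and for the second and third years".

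**The concern.** A percentage labelled month 12 should describe month 12. Under this rule it also depends on what happens afterwards and on how long the patient is watched. That length differs between landmarks, between analyses and possibly between groups. A later return to IgRT does not appear as a fall at the visit where it occurs; it lowers the figures for earlier visits. The quantity named in the objective is not reported directly.

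The curve raises a separate question. A patient who dies while on IgRT has no cessation event and fits only the rule for those still receiving it. If such patients are censored, the curve estimates cessation as though death had not intervened.

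Because the analysis is descriptive, the estimate is the result. What is at stake is the accuracy of a prominent estimate; no test or decision rule depends on it.

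**Working it through.** The documents give no target figure for this endpoint, so there is none to reproduce. They also give no restart rate, no follow-up distribution for the GOSH controls and no GOSH control mortality. The inputs below marked as assumed are illustrative.

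**1. Counting example (arithmetic only).** Take 10 patients (SAP 7.1: "The study protocol recruited 10 subjects with a diagnosis of ADA-SCID") followed to month 36. Suppose 7 are off IgRT at month 12 and 2 of these restart at month 20.

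| Month | 12 | 18 | 24 | 30 | 36 |
|---|---|---|---|---|---|
| Off IgRT at the visit | 7 | 7 | 5 | 5 | 5 |
| SAP rule, final analysis | 5 | 5 | 5 | 5 | 5 |

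At the primary analysis the SAP rule gives 7 at month 12 if neither patient has yet reached month 20. At month 18 the objective asks for 3/10 = 30% requiring IgRT; the complement of the SAP figure is 5/10 = 50%. In general, among patients followed to month 36, anyone off at t with no later restart is also off at every later landmark, so the count cannot fall.

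**2. Varying look-ahead.** Assume 70% off IgRT at every landmark and a constant restart hazard h per year. Then reported % = 70 × mean of exp(−h × look-ahead in years). With the look-ahead ending at month 36, the final-analysis look-aheads are 2, 1.5, 1, 0.5 and 0 years:

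| h per year | 12 | 18 | 24 | 30 | 36 |
|---|---|---|---|---|---|
| 0 | 70.0 | 70.0 | 70.0 | 70.0 | 70.0 |
| 0.02 | 67.3 | 67.9 | 68.6 | 69.3 | 70.0 |
| 0.05 | 63.3 | 64.9 | 66.6 | 68.3 | 70.0 |
| 0.10 | 57.3 | 60.2 | 63.3 | 66.6 | 70.0 |

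**3. Between groups at month 12, look-ahead ending at month 36, h = 0.05.** Assume even accrual over the 5-year recruitment period and control follow-up F uniform on 1 to 18 years.

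- HSCT, look-ahead min(2, F − 1): 63.7%
- IMP, primary analysis, min(2, U) with U uniform on 0 to 5: 64.6%
- IMP, 24-month analysis, min(2, 1 + U): 63.7%
- IMP, final analysis, 2 years: 63.3%

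The gap is about 1 point at most, and its sign changes between the primary and final analyses.

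**4. Revision of the month-12 figure.** With 7 of 10 counted as off at the primary analysis, the chance that at least one is reclassified by the final analysis is 1 − {E[exp(−h × max(0, 2 − U))]}^7. This is 5.4%, 12.8% and 23.5% at h = 0.02, 0.05 and 0.10. One such patient moves the result from 7/10 (exact 95% CI 34.8 to 93.3) to 6/10 (26.2 to 87.8).

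**5. Kaplan-Meier curve.** Suppose 70% stop IgRT by month 18 unless they die first, and all deaths come before any cessation. Censoring the deaths gives 1−KM = 70%, whatever the survival S. The share of treated patients who stop is 70% × S:

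- S = 90%: 63%
- S = 80%: 56%
- S = 67%: 47%

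If 40% of deaths fall instead between day 100 and month 18, these become 64, 58 and 50%. The 67% is the background matched-unrelated-donor series in Protocol 5.1.3 (n = 15), not the GOSH controls; the other survival values are assumed. In whole patients: with 15 treated, 5 early deaths and 8 of 10 survivors stopping, the curve gives 8/10 = 80% against 8/15 = 53%.

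**The case against.** The strongest reply is that the sentence lists months 12 to 36 and the visit schedule uses the same term for its columns, so the subsequent time points are naturally the listed visits. That reading is the better one, and on it the group comparison is barely affected (step 3). It does not remove the shrinking look-ahead, the revisions between analyses or the mismatch with the objective.

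A second reply is that durable cessation is a legitimate measure, and dropping later restarters is what it does. This stands for a durability measure with a fixed horizon. It does not supply the status at each visit that the objective names.

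On the curve, the SAP does not say that deaths are censored; that is an inference from the only rule given. The curve is optional, and survival is reported alongside it. SAP 10.1 also says that some specification detail moved to programming documentation, which is not available here. These points limit the weight of the second issue but do not settle how deaths are handled.

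A reader might infer that the rule biases the comparison in favour of gene therapy because controls may be followed for many years. At h = 0.05 an unbounded look-ahead would give the HSCT group 47% (follow-up uniform on 1 to 18 years) or 56% (1 to 10 years) at month 12, against 63 to 65% for IMP. The documents do not support that conclusion. It needs the less natural reading, an assumed restart rate running for many years and an assumed follow-up distribution. A 6-point gap under the month-36 reading (70.0 against 63.7) would require all on-study subjects to have only just reached month 12 together, which sits badly with 5 years of recruitment.

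**Conclusion.** The point holds in a limited form. The landmark percentage is a durable-cessation count whose look-ahead changes with landmark and analysis stage. It cannot show a decline among patients followed to month 36, can be revised after it is first reported, and does not directly answer the objective. At an assumed 5% yearly restart rate the distortion across landmarks at the final analysis is up to about 7 points (63 against 70%). The between-group effect is about 1 point if the look-ahead ends at month 36; if it is unbounded, longer HSCT follow-up could lower the HSCT figure by an amount the documents do not let us estimate.

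If deaths on IgRT are censored, 1−KM overstates the share of treated patients who stop, more so in the group with more early deaths. Under the unbounded reading that effect and the first could run in opposite directions, so the net direction cannot be signed. With no restarts and no deaths on IgRT, nothing changes. The SAP should be amended because this is the main secondary endpoint and the remedy is cheap; no test or decision is at risk.

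**What to change.** **Landmark table.** At each month t, take all treated patients whose potential follow-up (treatment date to data cut-off) reaches t, whether or not they died. Tabulate dead, alive on IgRT, alive off IgRT and unknown. Report alive off IgRT, with its exact CI, out of those with known status.

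The denominator must be set by potential follow-up, not by known status alone, because an early death is always known while a living patient who has not reached t is not. Example: at the primary analysis with even 5-year accrual, 60% of subjects have potential follow-up to month 36. With an assumed 20% early mortality and 70% of survivors off IgRT, known status alone gives 0.7 × 0.48 / (0.48 + 0.20) = 49%, against 0.7 × 0.8 = 56%.

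**Durability, if shown.** Use one fixed look-ahead in both groups and at all analyses, for example no restart by t + 6 months for t = 12, 18, 24 and 30, never beyond month 36. Restrict it to patients whose potential follow-up reaches t + 6 and count deaths as not durably off. In the step 3 model this gives 70 × exp(−0.025) = 68.3% in both groups at every analysis. List later HSCT restarts separately.

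**Curve, if drawn.** Use the Aalen-Johansen cumulative incidence of cessation with death as a competing event.

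**Cost.** A few lines of SAP text and slightly more programming. Some figures become less favourable, HSCT restarts after month 36 are only listed, and the month-12 durability figure at the primary analysis covers only patients with potential follow-up to month 18. No extra test is needed.

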### **8.3.2.3 Rate of Severe Infections**

Infections will be recorded as adverse events. The infections of interest in this study are severe infections or opportunistic infectious episodes, defined as infections requiring hospitalization or prolonging hospitalization and/or documented infections by opportunistic pathogens (e.g. interstitial pneumonia, intractable diarrhoea).

The number (%) of subjects reporting severe infections or opportunistic infectious episodes along with the number of events reported will be summarized for each of the IMP treated and HSCT control groups (data permitting). In addition, the infection rate will be calculated as the number of infections/the total follow-up time. The rate will be calculated both within each treatment group and for each individual subject. The subject infection rate will be summarized by treatment group using descriptive statistics. In addition to the rate for the entire follow-up period, the rate will be calculated for both the first 12 months following transplant and for the second and third years.

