## Trial design and methods: Summary flowchart of the patients treated with gene therapy

**Recruitment period:** 5 years

**Trial duration per participant:** From consent until 3 years post-infusion of transduced CD34+ cells

**Estimated total trial duration:** 8 years

**Planned trial sites:** Great Ormond Street Hospital for Children NHS Foundation Trust (single-site trial)

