## **3.2 Management options for ADA-SCID**

### **3.2.1 Haematopoietic stem cell transplantation for ADA-SCID**

Haematopoietic stem cell transplantation (HCST) is the treatment choice that is most widely available to most physicians and transplant centres. Until recently, data on the outcome of ADA-SCID transplants has been limited as most SCID transplant papers have presented data on the outcome of all SCID types rather than by specific molecular defect (Antoine et al., 2003). For these reasons, a multicenter retrospective study gathering data on outcome of haematopoietic stem cell transplantation for ADA-SCID has been conducted. In this study, we analysed outcome of HSCT in 106 patients with ADA-SCID who received a total of 119 transplants.(Hassan, 2012 )

Donor source had a major impact on the outcome of HSCT (fig 1). Overall survival was higher in Matched Sibling Donor (MSD) and Matched Family Donor(MFD) HSCTs (86% (42 patients) and 81% (12 patients) respectively). Comparison of survival outcomes in MisMatched Unrelated Donor (MMUD) and haploidentical transplants [29% (7 patients) and 43% (30

patients) respectively] to those of MSD HSCT showed a highly significant difference ( $p<0.0001$ ). Comparison of overall survival in MSD to MUD HSCT also showed a significant difference ( $p<0.05$ ). In haploidentical transplants, even though overall survival was 43%, stable engraftment was only noted in 11 (37%) patients. The majority of deaths in the Matched Unrelated Donor (MUD), MMUD and haploidentical transplants (HAPLO) were in the first 100 days after HSCT, with relatively few late deaths. The causes of death were mainly related to pneumonitis/respiratory failure and sepsis which formed over 50% of all deaths. Other major causes included graft versus host disease (15%) and fungal infection (11%).

**Figure 1:** Kaplan-Meier curve showing overall survival in relation to donor source. MSD—matched sibling donor; MFD—matched family donor; MUD—matched unrelated donor; MMUD—mismatched unrelated donor; HAPLO—haploidentical donor (data from manuscript in preparation).

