## 5.2 Secondary Endpoints

- Overall survival and event-free survival at 2 years and 3 years
- Frequency of infections (evaluated at 1, 2 and 3 years after treatment)
- TRECS after 2 years post-gene therapy
- Requirement for immunoglobulin replacement therapy (IgRT) and serum immunoglobulin levels for IgA, IgG and IgM.
- Feasibility of the transduction procedure assessed by availability of greater than  $0.5 \times 10^6$  CD34+ cells/kg after transduction; undetectable RCL (determined retrospectively); and CD45+ cell viability after transduction equal to or greater than 50%, in accordance with the final product release criteria. These data will be reviewed and interpreted by the PI and the study team and so will not be included in this SAP.

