## 6 Timing of Analyses

The statistical analyses of data from this study will be performed in four stages:

Interim look:

- Performed after all on-study subjects have completed 6 months of follow-up post infusion
- Descriptive statistics for all available data

- Comparisons between IMP treated subjects and HSCT control cohorts of demographics and overall survival

Primary analysis:

- Performed after all on-study subjects have completed 12 months of follow-up post infusion
- Descriptive statistics for all available data
- Comparison to HSCT control cohorts on overall and event-free survival at 12 months (primary efficacy endpoints), use of immunoglobulin replacement therapy (IgRT) and infection rate (key secondary endpoints).

Long-term follow-up analysis:

- Performed after all on-study subjects have completed 2 years of follow-up post infusion
- Descriptive statistics for all available data
- Comparison to HSCT control cohorts on overall and event-free survival at 2 years, use of immunoglobulin replacement therapy (IgRT) and infection rate (key secondary endpoints).

End of study analysis:

- Performed after all on-study subjects have completed the study (3 years of follow-up post infusion)
- Descriptive statistics for the complete study cohort
- Comparison to HSCT control cohorts on overall and event-free survival at 3 years, use of immunoglobulin replacement therapy (IgRT) and infection rate (key secondary endpoints).

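### SAP 8.3.2.3 plans several infection rates without naming the one to be compared with HSCT or giving any of them an interval, and two of them can mislead

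*SAP*

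**What the plan says.** SAP 8.3.2.3 counts infections that are severe or opportunistic and sets the rate: "the infection rate will be calculated as the number of infections/the total follow-up time". It continues: "The rate will be calculated both within each treatment group and for each individual subject". For the per-child values, "The subject infection rate will be summarized by treatment group using descriptive statistics"; SAP 8 lists these statistics as mean, SD, median, minimum, maximum and number. Beside the rate over all follow-up, "the rate will be calculated for both the first 12 months following transplant and for the second and third years". Three periods at two levels make six rates per group.

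SAP 6 plans a comparison with the HSCT cohorts at the primary, long-term and end-of-study analyses on "use of immunoglobulin replacement therapy (IgRT) and infection rate (key secondary endpoints". The endpoint in SAP 5.2 is "Frequency of infections (evaluated at 1, 2 and 3 years after treatment", and the matching objective in SAP 4.2 and Protocol 4.2.2 covers 3 years.

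On-study participation in the Protocol summary runs "From consent until 3 years post-infusion of transduced CD34+ cells". Protocol Appendix 8 takes HSCT controls transplanted at the centre in 2000-2016. SAP 8.2.16 takes their follow-up from the eCRF and sets no upper limit.

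SAP 8.3.2.3 gives no rate ratio, test or confidence interval. SAP 8.3.2.2 does plan exact 95% intervals for immunoglobulin use, the other key secondary endpoint.

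**The concern.** A rate over all follow-up averages early and late risk, weighted by how long each period was observed. If risk falls once immunity recovers, longer follow-up lowers the rate even though no child is better protected. Controls transplanted from 2000 on may have much longer follow-up than the 3 years of the on-study children. The gap may be wider still at the primary analysis, when on-study children need only 12 months.

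The mean of per-child rates has a different weakness. A child seen for a few weeks counts as much as a child seen for years, and a single infection in those weeks becomes a very large annual rate. Protocol 3.2.1 reports that most deaths after unrelated-donor and haploidentical transplants "were in the first 100 days after HSCT, with relatively few late deaths". Those are the donor types expected in the primary control population of SAP 7.1, which has no matched family donor.

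With no rate designated in advance, the one quoted could be chosen after the results are seen, and without an interval a reader could not judge how firm it is.

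**Working it through.** The documents give no infection rate, power or sample size for this endpoint, so there is no stated figure to reproduce. The check asks what each rate would show if both groups had the same risk at the same time since treatment.

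**Inputs from the documents.** On-study follow-up 3 years (Protocol summary); 10 on-study children (SAP 7.1); control transplants 2000-2016 with no cap on follow-up (Protocol Appendix 8, SAP 8.2.16); 66% survival after matched unrelated donor transplant (Protocol 3.2.1).

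**Assumptions.** The infection rates; control follow-up spread evenly over 1 to 17 years, mean (1 + 17)/2 = 9; 16 controls; early deaths on days 10 to 100.

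**1. Whole-follow-up group rate, no deaths.** With rate a in year 1 and b after, and every child followed at least 1 year, the expected group rate at mean follow-up T is [a + b(T - 1)]/T. For a = 1.5 and b = 0.2:

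- Gene therapy, T = 3: (1.5 + 0.4)/3 = 0.633 per year.
- HSCT, mean T = 9: (1.5 + 1.6)/9 = 0.344. Ratio 0.633/0.344 = 1.84.
- HSCT, all T = 16: (1.5 + 3.0)/16 = 0.281. Ratio 0.633/0.281 = 2.25.
- If a = b, the ratio is 1.00 at any T.

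| a, b | Gene therapy (T = 3) | HSCT (mean T = 9) | Ratio | HSCT (T = 16) | Ratio |
|---|---|---|---|---|---|
| 1, 0.1 | 0.400 | 0.200 | 2.0 | 0.156 | 2.6 |
| 2, 0.3 | 0.867 | 0.489 | 1.8 | 0.406 | 2.1 |
| 1, 0.5 | 0.667 | 0.556 | 1.2 | 0.531 | 1.3 |

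If risk falls again after year 3, the gap grows. Rates of 1, 0.5 and 0.25 per year (year 1, years 2-3, later) give 1.73-fold over the 1-17 year spread; 1.5, 0.5 and 0.1 give 2.46-fold; 2, 0.3 and 0.05 give 2.72-fold.

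**2. Windowed group rates.** With 1.5, 0.5 and 0.1 in both groups, year 1 gives 1.50 against 1.50 and years 2-3 give 0.50 against 0.50. Capping HSCT follow-up at 3 years brings the overall ratio to 0.97-1.00 across the patterns in step 1 with a separate rate after year 3, and constant risk.

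**3. Mean of per-child rates.** One infection with death at day 30, 60 or 100 gives 365.25/30 = 12.2, 365.25/60 = 6.1 or 365.25/100 = 3.7 per year. Take ten children: nine with one infection in 3 years, one with one infection and death at day 30.

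- Group rate: 10/(27 + 30/365.25) = 0.37 per year.
- Per-child mean: (9 × 1/3 + 12.175)/10 = 1.52. Median: 0.33.

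**4. Early deaths, simulated** (4,000 replicates, 10 gene-therapy children, 16 controls, 33% early deaths among controls, rates 1.5, 0.5 and 0.1).

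- Deaths unrelated to infection: the whole-follow-up per-child mean is 0.79 for HSCT (SD across replicates 0.54) and 0.83 for gene therapy (SD 0.17). In year 1 it is 1.49 against 1.50.
- Each early death carrying one extra infection: the year-1 group rate is 2.00 for HSCT against 1.50, a genuine excess of 2.00/1.50 = 1.33-fold. The year-1 per-child mean is 4.60 against 1.50, or 3.07-fold.

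The 12-month window therefore repairs the group rate but not the per-child mean.

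**The case against.** The strongest reply is that the needed comparison is already there. The same paragraph plans group rates for the first 12 months and for years 2-3, and step 2 shows that they are sound. The endpoint and objective are set at 1 to 3 years, so the windows fit them naturally and the whole-period rate looks supplementary. The median is already among the planned statistics. Protocol 8.9.2 describes the comparison with historical controls as descriptive at all stages, under its primary-endpoint heading. HSCT infection data are used only where they allow, and no success rule depends on this endpoint.

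Most of this stands, and it limits the point. A reader might infer that the comparison rests on mismatched follow-up, or that the whole-period rate is biased against gene therapy and the per-child mean against HSCT. The documents support neither. No rate is ranked first. The whole-period artefact needs a falling risk. The per-child mean is clearly inflated for HSCT only if early death goes with infection, and long follow-up pulls it the other way.

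Falling risk is itself plausible but not documented for the controls. Protocol 9.1.2 describes low lymphocyte counts for some months after PEG-ADA withdrawal in gene-therapy children, without infection rates. Protocol 3.2.1 concerns deaths in a multicentre series; it attributes over half of all deaths mainly to pneumonitis or respiratory failure and sepsis, which makes a link with infection credible but does not show one.

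The reply does not remove three gaps: no rate is designated, none has an interval, and an unweighted per-child mean remains in the plan.

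**Conclusion.** The point holds in this limited form. SAP 8.3.2.3 contains suitable group rates but neither names them as the key secondary comparison with HSCT nor gives them an interval.

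The whole-follow-up rate can separate groups with identical risk if risk declines. At assumed rates of 1.5 and then 0.2 per year, the gap is about 1.8-fold at a mean control follow-up of 9 years. The 2.3-fold figure is the worst case for those rates, because it gives every control 16 years, a length inferred from the transplant dates and not stated. Under constant risk there is no gap. Other assumed patterns move the size in either direction.

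The per-child mean is unstable whenever children die early, also within the 12-month window, and is inflated against HSCT if those deaths are linked to infection. The plan should be changed, but no primary conclusion depends on it.

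**What to change.** Amend SAP 8.3.2.3 as follows:

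- Name the group person-time rates for 0-12 and 12-36 months as the comparison with HSCT.
- For each window, report the rate ratio with a 95% CI, from a negative binomial model with log follow-up as offset, or exact Poisson if events are sparse. The Poisson interval ignores repeated infections in one child and may be too narrow; say so where it is used.
- Present per-child rates as median and range, or as a listing, without the mean.
- Label the whole-follow-up rate as descriptive and not for comparison between groups, or cap HSCT follow-up at 36 months.

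This needs no new data: the cost is SAP wording and slightly more analysis. The intervals will be wide. As an illustration with 10 and 16 fully observed children at 1.5 infections per year in year 1, the expected counts are 15 and 24. The SE of the log ratio is √(1/15 + 1/24) = 0.329, so a ratio of 1 would carry a 95% CI of about 0.52 to 1.91, before any allowance for clustering. That width is information the reader needs.
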